2 GENERAL CONSIDERATIONS FOR DATA ANALYSIS

The database will be locked and final analysis of the data will be performed after all subjects have completed the study, outstanding data queries have been resolved or adjudicated as unresolvable, and the data have been cleaned and finalized. The statistical analyses will be performed by Quartesian LLC, with approval of the Sponsor, using SAS Version 9.4 (or higher).

All tables, figures and listings will be produced in landscape format.

Subjects will be assigned to treatment group defined by the treatment the subject received in the double-blind phase of the previous study IPX203-B16-02 (IPX203 or IR CD-LD).

In general, all data will be listed by subject and visit/time point where appropriate. The summary tables will be stratified by, or have columns corresponding to, treatment groups. Total group will also be presented.

The total number of subjects in the treatment group (N) under the stated population will be displayed in the header of summary tables.

Data will be summarized using descriptive statistics for continuous variables. Unless otherwise specified, descriptive statistics will include number of subjects, mean, standard deviation, minimum, median and maximum. Number of subjects with missing values will also be displayed, but only if non-zero. The minimum and maximum statistics will be presented to the same number of decimal places as the original data. The mean and median will be presented to one more decimal place than the original data. The standard deviation will be presented to two more decimal places than the original data.

In summary tables of categorical variables, counts and percentages will be displayed. The count [n] indicates the actual number of subjects in a particular category, which should always be less than or equal to the total number of subjects

in the respective study group with known (non-missing) category [M]. Percentage will be obtained by: % = n/M*100. Unless otherwise specified, all percentages will be expressed to one decimal place.

In by-visit summaries, only data collected on scheduled visits/timepoints will be summarized. Data from unscheduled assessments will be included in listings and may be used in determination of baseline if applicable.

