2.1 Definitions of Baseline

Baseline is defined as the last assessment obtained prior to the first dose of the open-label drug in the study IPX203-B16-03.

The study eCRF does not explicitly capture when the subject took the first open-label study drug dose. It will be assumed that this dose is taken on the day of Visit 1 after all study assessments.

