5.1 Adverse Events

Adverse Events will be coded using the Medical Dictionary of Regulatory Activities (MedDRA) version 22.0 AE coding system for purposes of summarization.

Only Treatment Emergent Adverse Events (TEAE) will be used for the summary analysis, unless otherwise specified. An AE will be considered as treatment-emergent if the date of onset is on or after the date of the first open-label study drug administration in the study IPX203-B16-03 and no later than 1 day after the last study drug dose in the study. AEs with unknown start dates will be counted as treatment-emergent unless the AE resolution date is prior to the first open-label study drug administration date. If the AE start date is partially missing, the AE will be considered treatment-emergent, unless the month and year (when available) rule out the possibility that the event occurred post start of the open-label study drug and no later than 1 day after the last study drug dose.

A TEAE is defined as treatment-related if it is recorded as “possibly related” or “related” to the study medication on the eCRF. AEs recorded as “not related” or “unlikely related” will be considered not related. In case the relatedness was not assessed, the most conservative result (related) will be chosen for the analysis.

In summaries of TEAEs a subject experiencing the same AE (with the same preferred term) multiple times will only be counted once for that preferred term. Similarly, if a subject experiences multiple AEs within the same system organ class, that subject will be counted only once in that system organ class. When summarizing AEs by severity, only the most severe occurrence within the preferred term or system organ class will be used. Similarly, when summarizing AEs by relationship to study drug, only the most related occurrence within the preferred term or system organ class will be selected for displays in summary tables.

An overall summary will include, by treatment group and overall, the number and percentage of subjects reporting at least 1 TEAE in the following categories:

- Any TEAE
- Treatment-related TEAE
- Serious TEAE
- TEAE leading to discontinuation of the study drug
- TEAE leading to death.

The following TEAE frequency tables will be prepared summarizing the overall number of TEAEs, the number and percentage of subjects reporting at least one TEAE by MedDRA System Organ Class (SOC) and preferred term (PT), by treatment group and overall:

- All TEAEs
- Serious TEAEs

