- Treatment-related TEAEs
- AEs leading to discontinuation of the study medication
- TEAEs in subjects with COVID-19
- TEAEs by severity
- TEAEs by relationship to study drug.

TEAEs will also be presented by SOC, PT, treatment group and one of the following subgroups of AEs:

- Total daily dose on the day of AE onset, categorized as < 400, 400 to < 1000, 1000 to < 1400, 1400 to < 1800, 1800 to <= 2400, and >2400 mg
- Daily dosing frequency on the day of AE onset (2, 3, 4, etc. times a day)
- Time to first onset, defined as the study day of the first onset of AE of the given SOC or PT for the subject, categorized as <= 7 days, >7 to 30 days, >30 to 90 days, >90 to 180 days, and >180 days.
- Time period. In this analysis each AE will be assigned to all (possibly several) time periods as in the previous paragraph during which the AE was active (i.e. after onset and prior to resolution).

TEAEs will also be presented by SOC, PT, treatment group and one of the following subgroups of subjects:

- Age: < 65, ≥ 65 years old at Visit 1
- Sex: Males, Females
- Race: Caucasians, non-Caucasians
- Region: North America or Europe
- PD duration at Visit 1: <8 years or ≥8 years
- Concomitant medications: the following non-exclusive subgroups will be defined for subjects taking concomitant medications of the following categories:

- Amantadine
- selective MAOB inhibitors
- anticholinergic PD medications
- dopamine agonists
- others

Additional summaries of non-treatment-emergent AEs that started in the previous study IPX203-B16-02 will be provided:

- AEs that started in study IPX203-B16-02 and resolved in the current study vs. those that did not resolve, by SOC, PT and treatment at the onset of AE (IPX203 or IR CD-LD and both treatments together)
- AEs that started in study IPX203-B16-02 and ended in the current study vs. are ongoing at the end of the current study by SOC, PT and treatment at the onset of AE (IPX203 or IR CD-LD and both treatments together)

For this analysis AE will be defined as resolved if its outcome is recorded as “Recovered/Resolved” or “Recovered/Resolved with Sequelae” in the eCRF. All other AEs will be considered not resolved.

The summaries by SOC and PT will be ordered alphabetically by SOC and PT.

Additionally number and percentage of subjects with TEAE will be presented by preferred term only in the descending order of total frequency.

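### First-onset TEAE counts in intervals of 7 to about 90 days have no subjects at risk or person-time, so the row sizes mostly reflect interval length rather than the timing of risk

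*SAP*

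**What the plan says.** SAP 5.1 presents TEAEs by SOC, PT and treatment group under four classifications of the event itself:

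- the dose when it began ("Total daily dose on the day of AE onset, categorized as" six bands);
- the dosing frequency when it began;
- the study day of the subject's first onset of that SOC or PT, "categorized as <= 7 days, >7 to 30 days, >30 to 90 days, >90 to 180 days, and >180 days";
- the periods in which it was active, where "each AE will be assigned to all (possibly several) time periods".

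No number at risk, person-time or exposure-adjusted rate is planned for any of them. The general rules in SAP 2 give two denominators. One is the group size: "The total number of subjects in the treatment group (N) under the stated population will be displayed in the header of summary tables". The other is a head count among subjects with a known category: "Percentage will be obtained by: % = n/M*100". Neither is defined per interval or per dose band.

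SAP 3.3 summarizes treatment duration by group and total daily dose by visit, in the same six bands. It does not connect either to the adverse-event tables. Protocol 13.5 makes no adjustment for dropouts.

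**The concern.** Age group or sex is fixed for a subject, so a head count is a sensible denominator there. Time since first dose is different: every subject who stays passes through all five onset intervals, and the last is almost thirteen times as long as the first. A first-onset count therefore grows with the length of the interval. It also shrinks as subjects leave or have already had the event.

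The study's objective is long-term safety, and this is the table in which a reader will look for early, steady or late risk. As planned, steady risk looks late in the raw rows. A reader who divides by interval width sees a mild decline that need not be real.

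**Working it through.** **Inputs.** Interval edges are 0, 7, 30, 90 and 180 days (SAP 5.1). Nine months of treatment (Protocol synopsis) is taken as 270 days, so the widths are 7, 23, 60, 90 and 90 days, and 90/7 = 12.9. N = 300 is the protocol's enrollment estimate and is used only for scale. The documents give no adverse-event incidence and no dropout rate. I assume 9-month first-onset incidence F from 2% to 60% and dropout d of 0 or 20%. There is no plan figure to reproduce.

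**Model.** Constant hazard h = −ln(1−F)/270 and constant dropout hazard g = −ln(1−d)/270. For an interval starting at day a with width w:

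- share of subjects with first onset in it = exp(−(h+g)a) × h/(h+g) × (1 − exp(−(h+g)w));
- person-time at risk in it = that share divided by h.

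At F = 10%, h = 0.000390 per day; at d = 20%, g = 0.000826 per day.

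**Rows at constant risk** (percent of subjects with first onset):

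| F, d | ≤7 | >7–30 | >30–90 | >90–180 | >180 | >90–180 ÷ week 1 |
|---|---|---|---|---|---|---|
| 10%, 0 | 0.27 | 0.89 | 2.29 | 3.33 | 3.22 | 12.2 |
| 10%, 20% | 0.27 | 0.88 | 2.18 | 2.98 | 2.67 | 11.0 |
| 40%, 20% | 1.31 | 4.14 | 9.65 | 11.83 | 9.26 | 9.0 |
| 60%, 20% | 2.34 | 7.22 | 15.85 | 17.38 | 11.89 | 7.4 |

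At F = 2% without dropout the last column is 12.7. Over the assumed range it therefore runs from 7.4 to 12.7.

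**Where the ordering changes.** The >180 day row falls below the >30 to 90 day row once F passes about 49% (no dropout) or 36% (20% dropout). The two 20% dropout lines at F = 40% and 60% show this. The >90 to 180 day row remains the largest throughout the assumed range.

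**Dividing by width.** Last interval per day relative to week 1, with no true change:

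- F = 10%: (3.22/90)/(0.27/7) = 0.92 without dropout and 0.76 with 20% dropout (from unrounded shares);
- F = 20%: 0.83 and 0.69.

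**Dividing by person-time.** At F = 10% every interval gives 14.3 first events per 100 person-years, with or without dropout.

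**A true early excess, F = 10%.** If the week-1 hazard is doubled, the rows without dropout are 0.54, 0.89, 2.28, 3.32 and 3.21%. The excess does not stand out, although per day week 1 is 2.1 times the >90 to 180 day interval (2.4 with 20% dropout). If it is five-fold, the rows are 1.36, 0.88, 2.26, 3.30 and 3.18%, and the excess shows because week 1 exceeds the longer interval after it.

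**Precision, N = 300, F = 10%.** Week 1 holds about 5.7 person-years (300 × 7/365.25) and 0.8 expected first events. The >90 to 180 day interval holds 63 to 70 person-years and 9 to 10 events.

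**Dose and frequency at onset.** The ratio of two rows equals the rate ratio times the ratio of time spent in the two categories. The documents do not give those times, so no size can be computed.

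**The case against.** The interval limits are printed in the row labels, so a careful reader can divide by width. Treatment-group columns can be compared within one interval, so a week-1 effect of switching from IR CD-LD stays readable. Disposition, treatment duration and by-visit dose are summarized elsewhere. All of this stands, and it is why the point is about presentation.

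The residual decline is also small next to chance. With 0.8 expected events, week 1 is empty with probability exp(−0.8) = 0.45, and a count of 8 in the last interval has an exact 95% interval of about 3.5 to 15.8. That stands for a single AE of this size. It is weaker for commoner terms, where the residual decline is larger and counts are higher.

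Day 1 of the extension is not first exposure, because every subject had IPX203 in the parent study's dose conversion, and SAP 7 defers summaries over the whole IPX203 exposure to the ISS. That limits what onset time means here. It does not supply denominators for tables that remain in this SAP.

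A reader might infer that the late rows are always the largest. They are not: for very common terms, which is more likely at SOC level, the >180 day row drops below the >30 to 90 day row. A reader might also infer that the plan hides any early risk. The five-fold example shows that it does not. Nor do the documents support a stated bias in the dose or frequency tables, since time in each category is unknown.

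**Conclusion.** The point holds for the onset-interval table. No section supplies subjects at risk or person-time, and the SAP's own cut-points make the raw rows a poor guide to timing. At constant risk the >90 to 180 day row is about 7 to 13 times week 1, and the two rows after day 90 are the largest pair for terms below roughly 36% to 49% incidence. After division by width an apparent decline to 0.76 to 0.92 remains at 10% incidence.

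These sizes rest on assumed incidence and dropout, constant hazards and 270 days of follow-up; only the widths come from the SAP. The active-period, dose and frequency tables have the same gap, but its effect there cannot be quantified. No test, error rate or decision rule is affected. The consequence is possible misreading of a descriptive safety table, and the change is a worthwhile, inexpensive improvement.

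**What to change.** - **Onset intervals.** Keep the counts. For each interval add subjects at risk at its start, person-years at risk and first events per 100 person-years. Count time from first dose to the first event of that SOC or PT or to the end of the TEAE window ("no later than 1 day after the last study drug dose in the study"), whichever comes first. Show TEAEs of unknown onset date in a separate row, because SAP 5.1 can count them as treatment-emergent but they cannot be placed in an interval.
- **Active period.** Add the number of subjects under observation in each interval.
- **Dose and dosing frequency at onset.** Add only the person-years spent in each category, from the IPX203 Dose Adjustment Log, as context. Give no event rates. Note that dose follows response and tolerability (Protocol 6.5), so rates by dose band would invite a dose-response reading.

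**Cost.** A little programming and no new data: first and last dose dates already feed treatment duration, and the log already feeds the regimen-change summary (SAP 3.3). Rates in sparse intervals will be imprecise. Three events in week 1 would give 3/5.75 = 52 per 100 person-years, with an exact 95% interval of 11 to 153. Week-1 person-time is also approximate, because the first dose date is not recorded: "It will be assumed that this dose is taken on the day of Visit 1 after all study assessments".

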9.2. Concomitant Medications

9.2.1. Permitted PD Medications and Surgical Treatments

Concomitant therapy with amantadine, selective monoamine oxidase (MAO) type B inhibitors (eg, safinamide, selegiline, rasagiline), anticholinergic PD medications (eg, benztrapine, trihexyphenidyl), hypnotics (including low doses of quetiapine ≤ 25 mg per day), dopamine agonists, including apomorphine, supplemental CD, and COMT inhibitors are allowed provided the doses and regimens (and any adjustments) are recorded on the concomitant medication form. Implantation of a deep brain stimulator (DBS) for the treatment of PD is permitted during this study provided the stimulation settings are recorded.

Although apomorphine, supplemental CD, COMT inhibitors, and DBS were not permitted in Study IPX203-B16-02, these treatments may be initiated during the current study.

All concomitant medications taken during this study will be recorded.

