1.2 Study Design

Subjects who have successfully completed Study IPX203-B16-02 (A Randomized Controlled Study to Compare the Safety and Efficacy of IPX203 with Immediate-Release Carbidopa-Levodopa in Parkinson's Disease Patients with Motor Fluctuations) may be offered the opportunity to enroll in this 9-month, multicenter open-label study. The study consists of a baseline visit (Visit 1) followed by 3 visits (Visits 2 to 4) spaced at approximately 3-month intervals. For subjects who successfully complete Study IPX203-B16-02, the baseline visit (Visit 1) of this study will occur coincident with the End of Study (EOS) Visit 7 of the preceding study, (with an allowed window of + 7 days). After providing written informed consent (and signing Health Insurance Portability and Accountability Act [HIPAA] authorization for subjects at United States [US] sites only), confirmation of eligibility and baseline procedures will be performed. Subjects will be initially started on the final IPX203 dosing regimen that was determined during the IPX203 dose conversion period of Study IPX203-B16-02. Investigators are permitted to adjust the dosing regimen of IPX203 during this study to achieve the optimal balance of efficacy and safety and any changes will be recorded.

Subjects may continue to take their non-LD-containing PD concomitant medications (including dopamine agonists, amantadine, and selective monoamine oxidase-B (MAO-B) inhibitors [safinamide, rasagiline and selegiline]) during the study. Changes in doses or in dosing regimens of all non-CD-LD PD medications and/or the addition of new non-CD-LD PD medications will be captured. Supplemental CD and benserazide, apomorphine, and the addition of catechol-O-methyltransferase (COMT) inhibitors (eg, entacapone, opicapone, and tolcapone) can be initiated during the study.

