1.3 Sample Size and Power

This study is an open-label study in PD subjects. All subjects who successfully complete IPX203-B16-02 are eligible to enroll in this study; it was originally estimated that approximately 300 subjects would be enrolled, but a larger number could be enrolled.

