5.8 Concomitant Medications

Concomitant medications are defined as medications taken while a subject took the open-label study drug, i.e. medications with stop date on or after the date of the first administration of the open-label study drug or those that are ongoing.

Concomitant medications will be coded using WHO Drug Dictionary version March 2019.

Use of concomitant medications will be summarized by ATC class (the highest available level), preferred name and treatment group, as well as for both treatment groups combined. A subject reporting the same medication more than once will be counted only once for that medication name; similarly, a subject reporting several medications in an ATC class will be counted once for that class. The summary will be ordered alphabetically by ATC class and preferred name.

Concomitant medications will also be grouped into various anti-PD medication classes:

- Amantadine

- selective MAO-B inhibitors
- anticholinergic PD medications
- dopamine agonists
- others

as well as antidepressants, sleep aids, and others.

Frequencies and percentages of subjects taking these classes of medications as well as each medication preferred name under the class will be summarized by treatment group as well as for both treatment groups combined.

All concomitant medications will be listed.

6 COVID-19 considerations for analyses

As the study will be partly conducted during the COVID-19 pandemic, a number of visits can be delayed, canceled or conducted remotely. To account for these circumstances the following changes were implemented in analysis:

1. All measurements for the following scales that were done remotely due to COVID-19 will be included in the analysis as if they were done at a face-to-face visit:
 - C-SSRS (Columbia Suicide Severity Rating Scale)
 - NMSS (Non-Motor Symptom Assessment Scale for Parkinson's Disease)
 - PAS (Parkinson Anxiety Scale)
 - PDQ-39 (39-item Parkinson Disease Questionnaire)
 - PDSS-2 (Parkinson's Disease Sleep Scale-2)
 - PGI-S (Patient Global Impression of Severity)
 - GCSI (Gastroparesis Cardinal Symptom Index)
 - TSA (treatment Satisfaction Assessment)
 - ZBI-12 (12-item Zarit Burden Interview)
 - EMSQ (Early Morning Symptoms Questionnaire)
 - MDS-UPDRS parts I, II, and IV
2. Remote measurements, due to COVID-19, of the following scales will be excluded from all analyses:
 - MDS-UPDRS Part III
 - CGI-S (Clinical Global Impression of Severity)

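### The co-medication TEAE subgroups have no time anchor, so a drug started after an adverse event, or to treat it, counts as exposure for that event

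*SAP*

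**What the plan says.** SAP 5.1 lists subject-level subgroups for the TEAE tables. For co-medication, "the following non-exclusive subgroups will be defined for subjects taking concomitant medications of the following categories": amantadine, selective MAO-B inhibitors, anticholinergics, dopamine agonists and a residual class. No date or visit is attached.

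SAP 5.8 uses the same five classes. It takes a concomitant medication to be one used during open-label treatment, spelled out as "medications with stop date on or after the date of the first administration of the open-label study drug or those that are ongoing". The start date plays no part.

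The TEAE window opens at the first open-label dose and closes "no later than 1 day after the last study drug dose in the study". It is not linked to when a co-medication began.

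New drugs are expected. SAP 1.2 states: "Changes in doses or in dosing regimens of all non-CD-LD PD medications and/or the addition of new non-CD-LD PD medications will be captured". Protocol 9.2.1 notes that apomorphine, supplemental CD and COMT inhibitors were not permitted in the parent study but that "these treatments may be initiated during the current study".

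Other breakdowns in SAP 5.1 do have an anchor. Age is taken at Visit 1, as is disease duration ("PD duration at Visit 1: <8 years or ≥8 years"). IPX203 dose is classified by "Total daily dose on the day of AE onset", and dosing frequency likewise.

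**The concern.** Co-medication can change during the same 9 months in which events accrue. If membership of a subgroup is settled by use at any time on open-label drug, the event can come first and the exposure second. A subject with a TEAE in month 1 who starts a drug in month 8 is counted as a user with that event. If the drug was started to treat the event, the event itself caused the classification.

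Long-term safety is part of the study objective, and these are the SAP's only tables relating TEAEs to co-medication. A reader of the study report would naturally look in them for signs that a class adds risk on IPX203. An excess produced only by the order of events would look the same as a real one.

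**Working it through.** **1. No figure to reproduce.** The tables carry no test, effect size or power. The only number is an enrolment estimate in SAP 1.3: "it was originally estimated that approximately 300 subjects would be enrolled, but a larger number could be enrolled". The documents give no rate of co-medication use, of post-event starts, or of any TEAE. Every rate below is an assumption.

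**2. Time anchors in SAP 5.1.**

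| Factor | Anchor |
|---|---|
| Age, disease duration | Visit 1 |
| IPX203 dose, dosing frequency | Day of event onset |
| Co-medication class | None; SAP 5.8 sets no start-date condition |

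**3. Formula, with no true effect of the drug.** Let b be use at Visit 1, r the 9-month risk of the event, s1 the chance that a Visit 1 non-user with the event starts the class afterwards, and s0 the chance of a start in a Visit 1 non-user without the event. Then:

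- share of event subjects classed as users: u1 = b + (1 − b)s1
- share of event-free subjects classed as users: u0 = b + (1 − b)s0
- risk in users: r·u1 / [r·u1 + (1 − r)u0]
- risk in non-users: r(1 − u1) / [r(1 − u1) + (1 − r)(1 − u0)]

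**4. Worked case.** Take 300 subjects, r = 10%, b = 20%, s1 = 25%, s0 = 3%. Of 30 event subjects, 6 are users at Visit 1 and 25% of the other 24, again 6, start later: 12 users. Of 270 event-free subjects, 54 are users at Visit 1 and 3% of the other 216, about 6.5, start later: 60.5 users. Risk in users is 12/72.5 = 16.6%. Risk in non-users is 18/227.5 = 7.9%. The ratio is 2.09, although the drug does nothing.

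**5. Range at b = 20%, r = 10%.**

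| s1 | s0 | Users | Non-users | Ratio to non-users | Ratio to all subjects (10%) |
|---|---|---|---|---|---|
| 25% | 3% | 16.6% | 7.9% | 2.09 | 1.66 |
| 15% | 5% | 12.9% | 9.0% | 1.43 | 1.29 |
| 10% | 5% | 11.5% | 9.5% | 1.20 | 1.15 |

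The last column is the user risk divided by the overall 10%. It shows what a reader would see with no non-user column.

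**6. Dependence on use at Visit 1.** With s0 = 5%, s1 = 15% or 30%, and r = 5%, 10% or 20%:

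| b | Ratio, users to non-users |
|---|---|
| 0% | 2.3 to 6.4 |
| 10% | 1.6 to 3.2 |
| 30% | 1.3 to 2.0 |
| 50% | 1.2 to 1.6 |

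The row b = 0% describes a drug that can only start on study. If s1 = s0 = 5%, the ratio is 1.00 in every row.

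**7. Longer follow-up alone.** A simulation of a drug started only on study assumed starts unrelated to the event, a 20% event risk and a 10% start probability over 9 months. With dropout of 10%, 20% and 30%, the ratios were 1.02, 1.08 and 1.13.

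**8. Subgroup fixed at Visit 1.** In these scenarios the event risk does not depend on Visit 1 use, and later starts no longer affect classification. The ratio is therefore 1.00 by construction.

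**The case against.** The strongest reply has five parts.

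- **SAP 5.1 never says any on-study use.** True. That reading comes from applying SAP 5.8. But 5.8 is the only definition in the SAP, and no other text narrows it. It does exclude drugs started after the last open-label dose, but not drugs started between an event and that dose.
- **No risk ratio is planned.** This stands. The tables are counts and percentages, and no non-user group is named, so the contrast above is the reader's. Step 5 shows that a comparison with all subjects is also distorted, though less.
- **The rates are invented.** This stands. The distortion needs starts to be more frequent after an event than without one. Many preferred terms would not prompt a Parkinson's drug, and Protocol Appendix A, for slow or lost response and for dyskinesia, describes IPX203 adjustments and mentions no co-medication start. A reader might infer that the tables will show co-medication as harmful; the documents do not establish that.
- **Much use predates Visit 1.** Subjects may continue agonists, amantadine and MAO-B inhibitors, so the distortion may be small in those classes. Apomorphine, which Protocol 9.2.1 places among the agonists, would be diluted there by continuing users. Supplemental CD and COMT inhibitors have no named class and presumably fall in the residual one.
- **The listings allow a check.** Event dates and all concomitant medications are listed, so single cases can be traced. That does not correct the table.

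A reader might also infer that longer stay is itself a major source of bias. Step 7 shows it to be small.

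**Conclusion.** The definition is defective as written. Applying SAP 5.8 to the SAP 5.1 subgroups admits exposure that follows the event, while SAP 5.1 anchors comparable factors at Visit 1 or at event onset. The result can be a false association in descriptive safety tables. That a false association will occur, or will be large, is not shown.

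The size is unknown. Under assumed rates and no true effect, the apparent ratio against non-users is about 1.2 to 2.1 with 20% use at Visit 1, and 2.3 to 6.4 for a drug that can only start on study. It approaches 1 where most use predates Visit 1 and post-event starts are rare. These figures rest on the assumed rates and on a comparator that the SAP does not name. No primary conclusion depends on the tables, but the change is worth making before database lock.

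**What to change.** In SAP 5.1, define each co-medication subgroup by use of the class ongoing at Visit 1, and show non-users of that class at Visit 1 as the comparator. The protocol's schedule already records concomitant medications at Visit 1.

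Report subjects who start a class after Visit 1 separately. For them, count only TEAEs with onset on or after the drug's start date and while on the drug. Rates per subject-time on the drug are optional. Without them, the starters' percentages should not be set against those of the Visit 1 groups, because their time at risk is shorter.

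The Visit 1 rule is a sentence in the SAP. The starters' table needs one further derivation and a medication start date. Both documents say that additions are captured, but SAP 5.8 mentions only a stop date, so the start-date field should be confirmed.

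The downsides are fewer subjects in some classes, almost none at Visit 1 for the drugs newly permitted here, and some Visit 1 users who stop early but stay classified as users. The change repairs time order only; users and non-users at Visit 1 may still differ in other ways.
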